# 5.3 Vulnerable populations

This study will not enroll any vulnerable populations. As per the exclusion criteria, all enrolled participants will have the capacity to consent. Capacity will be determined by MD or PhD qualified research staff as per the legally specified criteria for determination of decision making capacity, assessed by verbal responses from the participant.

# 5.4 Strategies for Recruitment and Retention

Subjects will be approximately 48 women and men, age 18-70, with moderate to severe AUD and PTSD or subthreshold PTSD, recruited from the public through local media advertisements. Participants will be recruited between approximately November 2018 and August 2021.

48 men and women with moderate to severe AUD and comorbid PTSD or subthreshold PTSD will be recruited from the community and from local clinical programs. We will initiate contact with subjects through multimodal outreach including contacts with treating clinicians in medical and psychiatric clinics at the Cohen Veteran Center (600 recruited annually) and Military Family Clinic at NYUMC (500 enrolled annually); Manhattan VA, Bronx, Manhattan and Brooklyn VA PTSD clinics and other VA medical centers within the greater New York City area (over 1300 with PTSD and comorbid AUD); Women's Mental Health Consortium of NY, Derner Institute at Adelphi University; addiction services sites, including the detox unit and Chemical Dependency Outpatient Program at Bellevue (11,400 visits annually, combined), Psychiatry Outpatient Clinic and Primary Care Clinic at Bellevue hospital, addiction services at the Manhattan and Brooklyn VA, and at the Federally Qualified Health Center (FQHC), an outpatient psychiatry clinic at NYU Lutheran Medical Center (115,000 visits annually). Additionally, patients will be recruited at the Nathan Kline Institute/Rockland Psychiatric Center and Gouverneur Health. Fliers and brochures will be distributed by clinicians to potentially interested participants.

Clinicians will be asked to only refer individuals who they believe are appropriate for the study, can safely delay treatment for 24 hours and who are capable of deciding to participate. At the time of referral, clinicians will provide study staff with names, contact information, and relevant clinical information for interested patients, who will sign an authorization form allowing the clinic to release their relevant information to study staff. Once referrals are given, the study team will access EPIC to determine the participant's initial eligibility. [name] and the study coordinators will maintain relationships with clinicians at these institutions in order to generate referrals. Additionally, the study team will use NYU's DataCore service to gather information from EPIC for current NYU patients who may be eligible. Participants can be referred to the study by their physician, the clinic, or through DataCore reports. To gather the information from EPIC, DataCore will request a report. Data gathered will be used to identify subjects that did not opt out of being contacted for research, and who fit eligibility criteria for this study. The data gathered will include inclusionary and exclusionary criteria, including the following information:

## Inclusion Criteria:

#### -18-70 years old

WITH diagnosis of PTSD (Post Traumatic Stress Disorder) OR Acute Stress Disorder OR Adjustment Disorder AND Alcoholism OR Alcohol Use Disorder OR Alcohol Abuse WITHOUT a diagnosis of Schizophrenia OR

Version: 4.3 Bipolar I.

DataCore will request this information from EPIC monthly. Once a patient has been deemed potentially eligible for the study, and is also noted in EPIC as having consented to be contacted for research, approved staff will e-mail potential participants' treating physicians following scheduling the patient for their assessment visit. Approved staff will contact potential participants identified through EPIC by either email, MyChart, or by phone. Due to sharing the same recruitment resources, the phone consent and screen will be identical to those used in [name] study, s18-01405. Any recruitment information sent by email will use Send Safe email (or will be done through MyChart). Once contact is made, approved recruitment language will be used to communicate the reason for contact and potential participants will be asked if they are interested in participating in this specific study. If the potential participant requests information regarding opting out of further recruitment for all research, they will be directed to contact our team.

Active recruitment will also take place through social media sources, including Facebook, Twitter, Instagram, Reddit, Craigslist, clinical trial pre-screening services like StudyKik, Patient Wise, BuildClinical, and TrialFacts, online research recruitment sites such as ResearchMatch, VolunteerMatch ClinicalConnection, Antidote, and TrialSpark, online forums, local newspapers and other print media (i.e. Bushwick Daily, Queens Chronicle, New York Post, Schneps Media etc.), online periodicals such as Time Out Magazine, Military Times and Schneps media, radio advertisements within New York City, online targeted advertisement services from companies such as the Washington Post, email newsletters such as Division of Veteran Services, through academic email listservs (including Child and Adolescent Mental Health Studies [CAMS] listserv), at social service agencies, community mental health clinics, community organizations, local professional organizations, residential treatment facilities, consenting support and recovery centers, regional employee assistance programs, religious organizations, cultural centers, social clubs, local shops, and local universities. Fliers and brochures will be distributed by clinicians to potentially interested participants. Additionally, the study team will use NYU's DataCore service to gather information from EPIC for current NYU patients who may be eligible.

TrialFacts: TrialFacts is a referral service that targets advertisements to individuals who may be eligible for the study. Participants are provided with detailed information about the study and then complete a brief IRB-approved questionnaire. Participants who complete the questionnaire have consented to collection of their responses to the questionnaire, including their contact information, as well as TrialFacts' sharing their information with the study team. Trialfacts provides the study team with the respondents' questionnaire responses and contact information (name, phone number, email, state, zip code, gender, and DOB) if they meet minimum eligibility requirements via a restricted access spreadsheet. If not eligible, TrialFacts releases the questionnaire respondents' contact information. The study team may request ineligible respondents' contact information from TrialFacts to double-check on responses on an as needed basis.

Eligible, participants are invited to book an appointment for the phone screen using the TrialFacts online platform. If they do not book an appointment, the study team reaches out to the participant to schedule. If the participant chooses to book online, they are sent a calendar invitation and a confirmation email. With an online booking, TrialFacts sends the participant email reminders 24 hours and 1 hour before their phone screen appointment, and text message reminders 1 hour and 10 minutes before the phone screen appointment.

After the study team completes the phone screen, the restricted access spreadsheet is updated with participant's enrollment status and/or reason for exclusion in order to help TrialFacts better target audiences. The study team only indicates whether the participants was enrolled or not enrolled and which of the exclusion criteria were met. The reasons for exclusion on the spreadsheet are limited to: not enough drinking days; current life stressors; exclusionary medication; exclusionary medical condition; exclusionary psychiatric disorder; exclusionary treatment; drug use; no PTSD; age; scheduling; new treatment; unwilling to use contraceptives; recent trauma; behavioral concerns; and legal issues. No identifiers or health information are added to the spreadsheet.

Potential participants can either call the study line directly to speak with research staff or they can follow the link to a study screening questionnaire located at the bottom of the flyers and ads. The link re-directs to a secure, RedCap survey. Potential participants will indicate that they consent to complete the survey electronically before completing the questionnaire. Staff will contact respondents who meet minimum eligibility criteria via phone, email, and/or text message. Respondents will indicate their preferred method of contact on the RedCap survey.

BuildClinical: BuildClinical is an advertising and referral service that targets advertisements to individuals

#### #S17-00949

who may be eligible for the study. Study advertisements will be developed, IRB approved, and then optimally deployed across web platforms to target and engage the study population via the BuildClinical patient advertising network. Individuals who click on a BuildClinical ad will be redirected to a brief IRB approved REDCap questionnaire. BuildClinical provides the study team with the respondents' questionnaire responses and contact information (name, phone number, email, and state) if they meet minimum eligibility requirements via a HIPAA compliant internet portal. The internet portal is a one-way transfer of information from BuildClinical to the study team. The study team will not share any additional information with BuildClinical ads will be submitted to the IRB for approval prior to use.

All potential participants will be asked to complete a brief pre-screening interview either in person or by telephone, using an IRB approved, and scripted pre-screening form describing the basic facts of the study and inquiring about inclusion and exclusion criteria. (See request for waiver of authorization and waiver of documentation of consent). Study staff conducting the screening may ask follow-up questions or use the Timeline Followback tool to clarify responses and assess eligibility. An abridged version of the LEC (Life Events Checklist) will be completed during the pre-screening interview. Participants who pass the pre-screening interview (i.e., those who appear likely to qualify for the study and remain interested in participating) will be scheduled for a screening visit.

Individuals that do not pass the pre-screening or decline to enroll in the study will be asked whether they would like their information retained so they can be contacted for future research purposes. Participants may also optin to being re-contacted for the current study if their PTSD and/or AUD symptoms are near the inclusion threshold. If they decline, all information collected will be de-identified and all PHI information will be destroyed at the end of the study. The study team will have no linking information for those who fail the pre-screen or decline participation. If they assent to re-contact, PHI data collected on the initial screening form will be retained only for and shared with NYU-affiliated researchers strictly for the purpose of re-contacting for future research opportunities.

Participants in [name] clinical trial "Leveraging Biomarkers for Personalized Treatment of AUD Comorbid with PTSD" (IRB # s18-01405) who are determined to be ineligible will be evaluated for eligibility in this trial. Consenting participants' data will be linked to this study and procedures completed under the Biomarkers trial will not be duplicated for this trial except at PI or co-Investigator discretion.

Based on successful recruitment in current and past AUD and PTSD trials at NYULMC, we do not expect any significant barriers to recruitment. If recruitment lags, strategies would include altering staffing patterns and increasing advertisement and outreach to clinical programs. To maximize rates of completion of the follow-up visit, we will follow procedures that have been successful in retaining patients with similar demographics, e.g. drug using emergency department patients, for whom we have achieved follow-up rates of 85% at 6 months. If follow-up rates at 10 weeks are below 90%, we will reexamine our tracking procedures, and consider altering the reimbursement and/or completing community-based follow-ups.

We expect the population to be approximately 50% male, 50% female; 7% Hispanic, 60% Non-Hispanic Caucasian, 30% Non-Hispanic African American, and 3% other.

## 5.5 Duration of Study Participation

Including screening and follow-up visits, the total duration of participant involvement will be approximately 9 weeks. Total time of contact during these 9 weeks is estimated at 30-35 hrs.

## 5.6 Total Number of Participants and Sites

Recruitment will end when approximately 150 participants are enrolled. It is expected that approximately 48 participants who fully meet study criteria will be randomized in a 5:3 ratio to receive either 600mg CBD/day (PO) or placebo respectively (N=30 participants on CBD and N=18 participants on placebo).

## 5.7 Participant Withdrawal or Termination

#### 5.7.1 Reasons for Withdrawal or Termination

Participants are free to withdraw from participation in the study at any time upon request. An investigator may terminate participation in the study if:

• Any clinical adverse event (AE), laboratory abnormality, or other medical condition or situation occurs such that continued participation in the study would not be in the best interest of the participant

- The participant meets an exclusion criterion (either newly developed or not previously recognized) that precludes further study participation
- The participant fails to adhere to protocol requirements

## 5.7.2 Handling of Participant Withdrawals or Termination

Every effort will be made to undertake the protocol-specified safety follow-up procedures to capture AEs, SAEs, and UPs. The investigator will attempt to obtain at a minimum safety/survival data on all participants lost to follow-up. If a participant is lost to follow-up, they study team will attempt to contact the participant up to 15 times by telephone, email, or text message. If the participant fails to respond, locators identified by the participant at screening will be contacted up to three times in the method specified by the participant. If participants withdraw, are terminated, or are lost to follow-up prior to the end of the 6-week treatment phase (prior to T8), they will not be replaced to maintain 48 randomized participants to complete the 6-week treatment phase (through T8) and their partial data will be handled according to the statistical analysis plan (SAP).

# 5.8 Premature Termination or Suspension of Study

This study may be temporarily suspended or prematurely terminated if there is sufficient reasonable cause. Written notification, documenting the reason for study suspension or termination, will be provided by the suspending or terminating party to [name], NIH/NIAAA, the FDA, the DEA, and the NY State BNE. If the study is prematurely terminated or suspended, the PI will promptly inform the IRB and will provide the reason(s) for the termination or suspension. Circumstances that may warrant termination or suspension include, but are not limited to:

- Determination of unexpected, significant, or unacceptable risk to participants
- Demonstration of efficacy that would warrant stopping
- Insufficient compliance with protocol requirements
- Data that are not sufficiently complete and/or evaluable

Study may resume once concerns about safety, protocol compliance, data quality are addressed and satisfy the sponsor, IRB and/or FDA.

# 6 Study Agent (Study drug, device, biologic, vaccine etc.) and/or Procedural Intervention

# 6.1 Study Agent(s) and Control Description

The TN-C200M2 Oral Capsules and matching placebo for this study are provided by TilrayTM. The CBD is derived from cannabis and processed according to CGMP standards (see Quality Overall Summary document provided by Tilray). The active capsules will include CBD (the active ingredient) at a quantity of 200mg per capsule, as well as a mix of surfactants, co-surfactants, co-solvents and carrier oils. The placebo capsules will only include the same excipients, with no CBD.

# 6.1.1 Acquisition

The investigational product, CBD, will be imported from Tilray, which is located at [name]. The IND & DEA schedule I researcher, [name], will acquire a New York State Bureau of Narcotic Enforcement Class 9 license to import controlled substances as well as a DEA Schedule I import permit. Tilray will then obtain a DEA export permit that will allow them to ship CBD to [name]. Once all permits and licensure is in place, [name] will send a DEA 222 form to Tilray requesting the shipment of the investigational product. All shipping, importation and exportation of the investigational product will occur in line with local, state and federal regulations.

# 6.1.2 Formulation, Appearance, Packaging and Labeling

The drug product to be used in this study (TN-C200LM Oral Capsule) is a formulation of CBD dissolved in a mix of surfactants, co-surfactants, co-solvents and carrier oils at a concentration of 400mg/g. The formulation is designed to act as a self-emulsifying drug delivery system (SEDDS). Hard gelatin size-zero capsules are filled with the formulation to a fill weight of 500mg, providing a single capsule dose of 200mg CBD. This product in investigational and will be acquired as described above in 6.1.1. The TN-C200M2 Oral capsules are packaged in pharmaceutical grade 100mL polyethylene terephthalate (PET) bottles and lid, with a fill of 20 capsules.

#### 6.1.3 **Product Storage and Stability**

The study drug, CBD, will be stored securely by study personnel under the PI's individual schedule 1 DEA registration and New York Bureau of Narcotics Enforcement (BNE) class 7 license in accordance with all applicable laws and regulations. Additionally, a NYS BNE class 9 importer license and a DEA importer permit will be obtained prior to importation of study drug and study initiation. CBD will be stored in a double-locked refrigerator. The refrigerator is located in a designated research room with limited access to the PI and study staff only, within the NYU-HHC CTSI Facility, which is located at [name]. The drug is to be stored between 2-8 degrees Celsius. It is recommended that the investigational product be reassayed at 9-months. The Principal Investigator will oversee the appropriate storage, accountability and dispensing of the study medication and all study drug administration to the patients will be done by the PI or treating co-investigators.

Tilray™ has provided stability data for RSM-CBD Lots P56/8/116, P56/8/116, p56/17/017 and P56/44/057 at 4, 25 and 40 degrees Celsius. 12-months data has been generated on the first two batches and 9-months data has been generated on the second two batches. There is no evidence of degradation for any of the samples stored at 4, 25 and 40 degrees Celsius after 9-months. Additional and detailed stability data can be found in the accompanying Quality Overall Summary (QOS)document.

#### 6.1.4 **Preparation**

Because the investigational product is going to be shipped and received in its ready-for-dispensation formulation, there will not be any preparation required prior to dispensation. The study drug will be dispensed by qualified study personnel.

#### 6.1.5 **Dosing and Administration**

Participants will self-administer CBD vs Placebo twice daily for a total of 600mg/day CBD vs. Placebo for sixweeks. Participants will self-administer two 200mg capsules every morning following a light meal at approximately the same time of day, and an additional single 200mg capsule approximately 12 hours later following a light meal.

#### 6.1.6 Route of Administration

CBD will be administered orally in capsules that each contain 200mg CBD vs. Placebo.

#### 6.1.7 Starting Dose and Dose Escalation Schedule

All participants will receive 600mg/day CBD vs. Placebo for weeks 1-6 of treatment (T1-T8), unless contraindicated.

#### 6.1.8 **Dose Adjustments/Modifications/Delays**

If participants report AEs that are determined by the PI to be treatment-related during administration of study medication and are intolerable to the participant or represent a significant risk to the participant, daily administration will be reduced by 200mg/day every two days until symptoms are tolerable or clinical abnormalities are resolved. For self-described symptoms, tolerability will be determined by a joint decision between the PI and the participant, based upon of whether this symptom is tolerable or treatment related. For laboratory abnormalities, all values outside of the normal range will be regarded as presenting a risk, as evaluated by the PI. All reported AEs will be recorded. Dose will be titrated back up toward the full dose by 200 mg/day/week as tolerated, based upon a repeat assessment by the PI, including laboratory tests.

Individuals who cannot tolerate the 600mg dose will remain on their maximum tolerable dose for the remainder of the study. Treatment will be discontinued immediately if continuing the medication places the participant at significant risk in the medical judgement of the PI.

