# **3 Objectives and Purpose**

## 3.1 Primary Objective

The primary objective is to obtain a preliminary assessment of the safety, tolerability, efficacy, and effect size of CBD in reducing self-reported measures of alcohol use and PTSD symptoms in the AUD+PTSD/subthreshold PTSD population.

We predict that treatment with 600mg CBD daily will be well tolerated with no greater psychomotor or other motor side effects compared to treatment with placebo. We predict that CBD will be associated with a greater reduction in drinks per day and PTSD symptoms (total PCL-5 score) compared to placebo.

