As per Schedule I drug compliance, a biennial inventory shall be prepared and maintained in accordance with New York State and federal statutes. A copy of the inventory will be kept on file with other controlled substance records and shall be kept available for inspection for at least 5 years. The number of study drug-containing capsules will be checked on a weekly basis by two designated study staff members and it will be recorded on a Controlled Substance Accountability Log which includes the following information: 1) date and time of recording, 2) name of controlled substance, 3) amount received (number of capsules), 4) amount dispensed, and 5) amount returned. All other information will be included in the Study Drug Dispensation Log as each individual subject's dose is dispensed. The information included in the Study Drug Dispensation Log is: 1) subject initials/number (plus date of birth as a double identifier), 2) date and time of study drug dispensation, 3) drug name, 4) lot number, and 5) dose. Two designated study team members will sign the Study Drug Dispensation Log. The balance of the remaining medication and any amount returned will be recorded in the Controlled Substance Accountability Log (see above).

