# **12 Monitoring Adverse Events**

The investigator will follow all AEs until the event is resolved, stabilized, or the subject is lost to follow-up. Relevant
clinical assessments and laboratory tests may be performed as determined by the PI or a qualified designee, appropriate medical intervention should be provided and, if necessary, the subject may be excluded from additional treatment with the study drug.

Any actions taken and follow-up results must be recorded on the appropriate page of the CRF and in the subject's source documentation. Follow-up laboratory results should be filed with the subject's source documentation.

For all AEs that require the subject to be discontinued from the study, relevant clinical assessments and laboratory tests will be repeated as clinically appropriate, until final resolution or stabilization of the event(s).

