## 20.2 Statistical Hypotheses

Hypothesis 1a Safety and tolerability: CBD will be safe and well tolerated and will not lead to increased plasma THC. No clinically significant cognitive or motoric impairments, CBD-related serious adverse events, persisting adverse effects or treatment associated increases in plasma THC will be observed.

Hypothesis 1b: Alcohol use. Relative to the placebo-treated group, CBD-treated participants will have fewer drinks per day during the 6 weeks of treatment with CBD vs placebo.

Hypothesis 2: PTSD symptoms. Relative to the placebo-treated group, CBD-treated participants will lower PTSD symptoms during the 6 weeks of treatment with CBD vsplacebo.

Hypothesis 3a: Mechanism, traumatic stress-induced craving: Relative to placebo, CBD will be associated with a greater reduction between baseline and end of treatment in trauma induced alcohol craving, negative emotion, and psychophysiological arousal in response to the task.

Hypothesis 3b: Mechanism, AUD and PTSD related measures and cognition: Relative to placebo, CBD will improve self-report measures of craving, anxiety, mood, self-efficacy and cognitive performance.

Hypothesis 3c: Mechanism, anandamide: Relative to placebo, CBD will be associated with a greater increase

Hypothesis 4: CBD plasma levels. Within-group plasma CBD levels will stabilize within one week, i.e. 45 minutes post-CBD dosing levels obtained after 1 week of treatment will not differ from those obtained after 4 weeks of treatment at each dose.

Exploratory Hypothesis 1: Relationship between effects on PTSD symptoms and alcohol use. The onset of reduction in PTSD symptoms will precede the onset of reduction in alcohol use.

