### 20.3.2 Analysis of the Primary Endpoint(s)

For Hypothesis 1a, Safety and tolerability, the frequency of adverse events will be analyzed for the entire sample at all time points, tabulated for each treatment group, and compared using chi-squared tests. The safety analysis will be largely descriptive of outcomes for the entire study population. The incidence of AEs will be summarized by system organ class, preferred term, the likelihood of its relationship to the treatment, and severity for each treatment group. Clinical laboratory data will be summarized by type of test. Frequency and percentage of patients whose values fall outside of reference ranges will be presented for each measurement.

For Hypothesis 1b, Alcohol Use. The Primary outcome measure, number of drinks per day, will be analyzed with an MMRM to assess differences in change from baseline. The primary contrast is change from baseline (B1) at week 6 (T8). The model at each time point will include terms for treatment, time and treatment by time interaction as factors and the baseline value for each score as a covariate. Parameter estimation will be based on REML and to begin an unstructured covariate matrix will be used. If the model fails to converge, the form of the covariance matrix will be chosen based on Akaike's Information Criteria, and Schwarz' Bayesian Criterion. Model-based LS means will be obtained for change from baseline to each time point for each treatment group. At each time point, contrasts between CBD and placebo will be obtained. Secondary alcohol use measures will be tested with MMRM sequentially in a closed testing union intersection paradigm in the order listed in section C.8.3. Validity of the p-value will extend until the first test fails to have a p-value smaller than a two-sided alpha of 0.05. The analyses will continue for all measures but the resulting p-value will be nominal.

For Hypothesis 2, PTSD symptoms, the primary outcome measure, total score of the PCL-5, will be analyzed in the same way as the primary outcome for alcohol use. The primary contrast is change from baseline (B1) at week 6 (T8).

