#### 20.3.5 Adherence and Retention Analyses

Adherence to the protocol will be assessed with a smartphone-assisted medication adherence platform [94] in which the subject takes a video of drug administration at each dose, and transmits this to study personnel.

This program has been used successfully in previous studies, and includes security provisions that ensure protection of confidentiality and privacy. If the participant is unable to use the smartphone-assisted platform then medication adherence will be ensured using pill counting and meeting with the study nurse practitioner

Number of participants that complete the treatment phase of the study (through T8), complete the follow-up phase of the study (through T10), and are lost to follow-up will be collected. Frequency of and reasons for discontinuation of the intervention or study follow-up will also be tallied.

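### Dose reductions are recorded but never summarised, and no criterion ties tolerability to staying on 600 mg, so that dose could be reported as tolerated when a material share could not stay on it

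*Combined protocol and SAP*

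**What the plan says.** The primary objective (3.1) includes the prediction "We predict that treatment with 600mg CBD daily will be well tolerated", and adds that motor side effects should be no greater than on placebo.

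Section 6.1.8 provides for reduction when treatment-related events are intolerable or a significant risk: "daily administration will be reduced by 200mg/day every two days until symptoms are tolerable or clinical abnormalities are resolved". It allows stepwise return as tolerated, and then says: "Individuals who cannot tolerate the 600mg dose will remain on their maximum tolerable dose for the remainder of the study".

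Hypothesis 1a (20.2) gives safety and tolerability this content: "No clinically significant cognitive or motoric impairments, CBD-related serious adverse events, persisting adverse effects or treatment associated increases in plasma THC will be observed".

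The planned outputs are:

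- **Adverse events (20.3.2, repeated in 20.3.4):** "The incidence of AEs will be summarized by system organ class, preferred term, the likelihood of its relationship to the treatment, and severity", by arm, with chi-squared tests, plus out-of-range laboratory values.
- **Other safety (20.3.4):** means and SDs of plasma CBD and THC in the CBD arm by visit, and the number passing sobriety tests within two hours of the first dose at T1.
- **Retention (20.3.5):** completers through T8 and T10, losses to follow-up, and "Frequency of and reasons for discontinuation of the intervention or study follow-up will also be tallied".

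Information on reductions is collected. Section 12 requires that "Any actions taken and follow-up results must be recorded on the appropriate page of the CRF", and the dispensation log in 6.2 holds "2) date and time of study drug dispensation, 3) drug name, 4) lot number, and 5) dose".

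**The concern.** The protocol makes a prediction about a named dose and also names the event that most directly contradicts it: a participant who cannot tolerate that dose and is moved to a lower one. One would expect that event to be counted, and it is not. Nor does Hypothesis 1a require that participants stay on 600 mg.

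At stake is the statement the trial will make about its study dose. A report could follow the plan exactly, show full completion and no breach of Hypothesis 1a, and conclude that 600 mg is tolerated, although a sizeable part of the CBD arm finished on less. Section 20.4 says the trial is meant to support planning of confirmatory trials. Whether 600 mg can be sustained for six weeks is basic to that planning.

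**Working it through.** **The plan's own figure.** The documents state no figure on this point. The effect size in 20.4 concerns a comparison of means and does not enter here.

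**Step 1: follow one participant through the plan.** Suppose a CBD participant has a moderate, non-serious, treatment-related event judged intolerable, is stepped down to 200 mg, recovers, and stays at 200 mg through T8.

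| Planned output or criterion | What it shows for this participant |
|---|---|
| Hypothesis 1a: cognitive or motor impairment | No breach, unless the event was of that kind |
| Hypothesis 1a: CBD-related serious event | No breach; event not serious |
| Hypothesis 1a: persisting effect | No breach; event resolved |
| Hypothesis 1a: rise in THC | Not affected by the reduction rule |
| AE table (20.3.2, 20.3.4) | One moderate related event; dose and action taken not shown |
| Sobriety tests at T1 (20.3.4) | Measured at the first dose, before any reduction |
| Plasma CBD by visit (20.3.4) | Contributes to an arm mean; the reduction is not identified |
| Retention (20.3.5) | A completer, not a discontinuation |

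The event is visible. The failure to stay on 600 mg is not.

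**Step 2: look for another place where dose is used.** Section 20.3.3 says effects of dose will be assessed for anandamide and, by cross-reference, for plasma CBD and THC. That does not extend to tolerability.

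**Step 3: laboratory-driven reductions.** Section 6.1.8 regards any out-of-range laboratory value as presenting a risk, as evaluated by the PI. Section 10.4 does not count a laboratory abnormality as an adverse event unless it has clinical sequelae, which include an intervention. It does not say whether a dose reduction is such an intervention. Some laboratory-driven reductions may therefore appear only as an out-of-range value.

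**Step 4: size, by illustration.** Inputs: n = 30 in the CBD arm (20.5.1). The number reduced is an assumption, because the documents give none. The exact (Clopper-Pearson) 95% interval for x of n runs from the 2.5% quantile of Beta(x, n − x + 1) to the 97.5% quantile of Beta(x + 1, n − x). For x = 0 the lower limit is 0 and the upper limit is 1 − 0.025^(1/30) = 0.116.

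| CBD participants reduced, none discontinued | Discontinuation tally | Share reduced below 600 mg |
|---|---|---|
| 0 of 30 | 0/30: 0% (0% to 11.6%) | 0% (0% to 11.6%) |
| 3 of 30 | 0/30: 0% (0% to 11.6%) | 10% (2.1% to 26.5%) |
| 6 of 30 | 0/30: 0% (0% to 11.6%) | 20% (7.7% to 38.6%) |
| 9 of 30 | 0/30: 0% (0% to 11.6%) | 30% (14.7% to 49.4%) |

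The planned tally is the same in every row.

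**The case against.** The strongest reply is that the safety plan is broader than a count of discontinuations. A reduction for an adverse event follows one that has already occurred; 6.1.8 and section 10 require it to be recorded, and the tables show it by arm, severity and relatedness. Plasma CBD is summarised through T8. Hypothesis 1a has stated criteria of its own. Comparing participants as randomised, with permitted dose changes, is a normal intention-to-treat analysis. The safety analysis is meant to be largely descriptive, and 20.1 leaves a formal SAP to be written before lock and unblinding.

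Much of this stands, and it rules out several stronger readings that a reader might infer:

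- **That only discontinuations are tallied, or that intolerance enters no result.** The adverse event and laboratory tables contradict this.
- **That reductions remove the events from the results.** The triggering adverse event stays in the incidence table. A reduction can limit only later recurrence or duration.
- **That anyone reduced after about week 4 cannot be back at 600 mg by T8.** This holds only for a reduction to zero: restarting at 200 mg and rising by 200 mg/day each week takes 14 days to reach 600 mg. From 400 mg, one step takes 7 days.
- **That keeping reduced participants in the CBD arm is an error.** It is sound. The issue is what is then said about 600 mg.

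The reply does not close the gap. Intolerability under 6.1.8 is a joint decision of PI and participant for self-described symptoms, separate from the severity scale in 11.2, so a severity table cannot be converted into a count of those who left 600 mg. The pending SAP is an opportunity to add that count, but nothing in the present text commits to it.

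**Conclusion.** The point holds as a gap between the claim about a named dose and the outputs planned to support it. Reductions are recorded but no summary is planned, adverse events are not linked to the dose taken, and no Hypothesis 1a criterion depends on remaining on 600 mg. Followed as written, the plan could support a conclusion that 600 mg was tolerated when a material share could not stay on it.

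The size cannot be known from the documents. The range of 3 to 9 reduced among 30 (10% to 30%) is an assumption chosen to show that the discontinuation tally does not respond. It is not a forecast. The illustration also assumes no discontinuations and all 30 planned CBD participants. If no one is reduced, the gap has no consequence.

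This should be corrected before unblinding. It does not undermine the adverse event analyses already planned.

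**What to change.** In 20.3.2, alongside the existing adverse event analyses for Hypothesis 1a, and in the SAP promised in 20.1, prespecify by arm:

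1. The number and proportion with any reduction, interruption or stop of study medication for an adverse effect or laboratory abnormality, with reasons.
2. The proportion still on the full assigned three capsules per day at T8.
3. Exact 95% confidence intervals for each proportion, and the difference between arms.
4. Dropouts for other reasons, reported separately so that they are not read as intolerance.

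Base any statement that 600 mg was tolerated on these figures together with the adverse event tables. The placebo capsules match, so the same measure can be derived in both arms.

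The main source should be the record of actions taken on the CRF (section 12), supplemented by the dispensation log (6.2) and pill counts (6.3.2). The log alone is not enough: medication is supplied for one or two weeks at a time, so it cannot date steps made between visits.

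No change to the clinical reduction rule is proposed. The cost is a little more derivation work, and the stated tolerability may look less favourable.
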